9.2. Pharmacokinetic Analyses

Serum concentration and PK parameter data will be analyzed using the Pharmacokinetics Analysis Set.

9.2.1. Analysis of Serum Concentrations of BIO89-100

The serum concentration of BIO89-100 over time will be listed and plotted by individual and also summarized by treatment group. Serum concentration data will also be presented using arithmetic statistics.

9.2.2. Analysis of PK Parameters

The following PK endpoints will be summarized by treatment group:

- C_{max} within a dosing interval (Day 1 and Day 29), the maximum serum concentration within each dosing interval.
- $AUC_{0-\tau}$ within a dosing interval (Day 1 and Day 29), derived using linear-log trapezoidal rule; assuming linear curve when concentrations are increasing and exponential decay when concentrations are decreasing.
- t_{max} , the time at which C_{max} is observed in reference to the start of the dosing interval during dosing interval (Day 1 and Day 29).
- $t_{1/2}$, the time at which the concentration is half of the observed maximum concentration within the dosing interval during dosing interval (Day 1 and Day 29).

PK parameters will be calculated separately by designee of 89bio.

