
 To characterize BIO89-100 PK 	
 Maximal observed serum concentrations (C_{max}) within a dosing interval Area under the serum drug concentration by time curve within a dosing interval ($AUC_{0-\tau}$) Time to achieve C_{max} (t_{max}) Terminal elimination half-life ($t_{1/2}$) 
Additional PK parameters may be calculated if deemed appropriate.
 
The serum concentration-time data may also be used for population PK modeling with the results reported separately from the clinical study report.

Secondary	

¹ Resolution of NASH includes the total absence of ballooning (score=0) and absent or mild inflammation (score 0 to 1) associated with at least a 2 point reduction in NAS, and no worsening of fibrosis (progression ≥ 1 stage).

Objectives	Endpoints

 • To evaluate the immunogenicity of BIO89-100 as measured by presence of anti-drug antibodies (ADA) 	
 • Assessment of the incidence and characteristics of ADA after dosing (e.g., titer and/or binding specificity, to the FGF21, PEG part of BIO89-100, and neutralizing immunogenicity) • Impact of the presence of ADAs on serum BIO89-100 concentrations and clinical safety 
Additional ADA assessments will be performed if a severe hypersensitivity reaction (e.g., anaphylaxis) is observed.

 • To characterize biomarkers, PD profile, and biological activity of BIO89-100 administered at ascending doses and with both QW and Q2W dosing intervals • To evaluate the time, dose, and exposure relationship of BIO89-100 on biological activity, as assessed by biomarkers and PD 	
Change and percentage change from baseline in the following biomarkers/PD parameters:
 
 • Anthropomorphic measurements: 
 – Body weight • Laboratory parameters: 
 – Triglycerides – Non-high density lipoprotein (non-HDL) cholesterol – High density lipoprotein (HDL-c) – Low density lipoprotein (LDL-c) – Hemoglobin A1c (HbA1c) – Homeostatic model assessment of insulin resistance (HOMA-IR) – Liver function tests: alanine transaminase (ALT), aspartate transaminase (AST) – Adiponectin – N-terminal propeptide of type III collagen (Pro-C3) – Free fatty acids and Adipo-IR (fasting free fatty acids × fasting insulin) • Imaging measures:

Objectives	Endpoints

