7.5. Pharmacokinetics

Blood samples for analysis of BIO89-100 serum levels will be collected at the timepoints designated in the SoAs (Table 3 for Cohorts 1-4, Table 5 for Cohorts 5-6, and Table 6 for Cohort 7).

Blood samples will be processed for collection of serum fractions for determination of BIO89-100 serum concentrations. Serum samples will be shipped to the bioanalytical laboratory for analysis.

The trough serum BIO89-100 concentrations will be summarized by treatment group and nominal sampling time using descriptive statistics.

Pharmacokinetic parameters calculated by noncompartmental methods from the BIO89-100 serum concentration data will include:

PK Parameter	Cohorts 1-3	Cohorts 4-5
C_{max}	Within 1 st and 5 th dosing intervals	Within 1 st and 3 rd dosing intervals
$AUC_{0-\tau}$	Within 1 st and 5 th dosing intervals	Within 1 st and 3 rd dosing intervals
t_{max}	Within 1 st and 5 th dosing intervals	Within 1 st and 3 rd dosing intervals
$t_{1/2}$	Within 1 st and 5 th dosing intervals	Within 1 st and 3 rd dosing intervals

Additional PK parameters may be calculated if deemed appropriate.

The serum concentration-time data may also be used for population PK modeling with the results reported separately from the clinical study report.

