| MedDra | medical dictionary for regulatory activities |
| MMRM | mixed model repeated measures |
| MNAR | missing not at random |

| | |
|-----------|--|
| MRI-PDFF | magnetic resonance imaging – proton density fat fraction |
| n | sample size |
| NAFLD | nonalcoholic fatty liver disease |
| NASH | nonalcoholic steatohepatitis |
| non-HDL | non-high density lipoprotein |
| OGTT | oral glucose tolerance test |
| P1NP | n-terminal propeptide of type 1 collagen |
| PD | pharmacodynamics |
| PEG | polyethylene glycol |
| PIIINP | Amino-terminal propeptide of type III procollagen |
| PMM | pattern-mixture model |
| Pro-C3 | n-terminal propeptide of type iii collagen |
| PT | preferred term |
| Q2W | every two weeks |
| QTcF | corrected qt interval by Fridericia |
| QW | weekly |
| SAEs | serious adverse events |
| SAP | statistical analysis plan |
| SC | subcutaneous |
| SD | standard deviation |
| SE | standard error |
| SMC | safety monitoring committee |
| SOC | system organ class |
| $t_{1/2}$ | half-life |
| TB | total bilirubin |
| TEAE | treatment-emergent adverse event |
| TIMP-1 | tissue inhibitor of metalloproteinase 1 |
| t_{max} | time to maximum concentration |
| TSH | thyroid stimulating hormone |
| ULN | upper limit of normal |
| VCTE | vibration-controlled transient elastography |
| WHO | world health organization |
| WOCBP | women of child-bearing potential |

1. Introduction

This statistical analysis plan (SAP) describes the statistical methods and procedures to be implemented in clinical study BIO89-100-002. This statistical analysis plan is based on study protocol BIO89-100-002 Version 3.0 dated 25 March 2020. If the data suggest and warrant it, deviations from this plan will be considered. However, any deviations from the SAP must be substantiated by sound statistical rationale and documented in the final clinical study report.

2. Study Objectives

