4.1.2. Pharmacokinetic Endpoints

The primary pharmacokinetic endpoints are:

- Maximum concentration (C_{max}) on Day 1
- C_{max} on Day 29
- Area under the curve since last dose ($AUC_{0-\tau}$) on Day 1
- $AUC_{0-\tau}$ on Day 29
- Time to maximum concentration (t_{max}) on Day 1
- t_{max} on Day 29
- Half-life ($t_{1/2}$) on Day 1
- $t_{1/2}$ on Day 29

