5.20. Definition of Actual Time

For PK analysis, actual time will be defined as:

Actual Time=Actual Sample Collection Time - Actual Last Dosing Time (before the corresponding sample collection)

6. Potential Covariates

The stratification factor of biopsy confirmed NASH with fibrosis status (F1, F2, F3) Yes or No will be considered as a potential covariate to be adjusted for in the statistical models.

Subgroup analyses will be descriptive in nature.

8. Analysis Populations

The number of subjects in each analysis population by treatment group will be summarized.

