9.5.7. Immunogenicity Analyses

Results of immunogenicity assessment will be summarized by displaying the number of subjects with positive and negative tests. Antibody titers will be listed. Available binding specificity will be listed.

10. Changes to Planned Analysis in the Protocol

There are no changes to the planned analysis in the protocol.

11. Statistical Software

All statistical analyses will be performed using SAS version 9.4 or higher.

12. References

National Heart, Lung and Blood Institute (2020). *Low Blood Pressure*. Retrieved May 19, 2020, from <https://www.nhlbi.nih.gov/health-topics/low-blood-pressure>.

13. Appendix

Table 2 Schedule of Activities for Cohorts 1-4

| Cohorts 1-4 Assessments | Screening Period | | | Treatment Period | | | | | | FU Period | |
|---|------------------|---|----------------|------------------|--|---|---|---|---|-----------|---|
| Study Visit | | | | | | | | | | | |
| Study Day | | | | | | | | | | | |
| Informed consent | X | | | | | | | | | | |
| Medical history/demographics | X | | | | | | | | | | |
| Percutaneous liver biopsy (optional) ^b | X | | | | | | | | | | |
| Prior medications | X | | | | | | | | | | |
| Inclusion and exclusion criteria | X | | X | | | | | | | | |
| Complete physical exam ^c | X | | | | | | | X | | X | X |
| Symptom-directed physical exam ^d | | X | B | P | | B | B | B | B | | |
| Body weight ^e | X | | B | | | B | B | B | B | | |
| Waist and hip measurements | X | | B | | | | | | B | | |
| Fibroscan ^f | X | | | | | | | | | | |
| 12-lead ECG (single) ^g | X | | B | X | | B | B | B | B | X | |
| Urine drug screen and alcohol breath test | X | | X ^h | | | | | | | | |
| Clinical laboratory tests ⁱ | X | X | B | X | | B | B | B | B | X | |
| Cortisol (24 hour urine collection) ^j | X | | | | | | | | | | X |
| Urinalysis | X | | X | | | | | | X | | |
| HbA1c | X | | X | | | | | | | | X |
| Serology ^k | X | | | | | | | | | | |
| TSH | X | | | | | | | | | | |

| Cohorts 1-4 Assessments | Screening Period | | Treatment Period | | | | | | | | | | | | | | FU Period | | | | | | | | | | | | | | | | | |

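### The Part 1 SAP defines t1/2 as the time at which concentration is half of Cmax, which is not the terminal elimination half-life that the protocol names as a primary PK endpoint

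*SAP*

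**What the plan says.** The Synopsis of the protocol lists t1/2 among the Part 1 primary PK endpoints and names it "Terminal elimination half-life"; the glossary (Appendix 6) expands the symbol the same way. Section 7.5 places t1/2 in a table introduced by "Pharmacokinetic parameters calculated by noncompartmental methods from the BIO89-100 serum concentration data will include", to be obtained within the first and the fifth (or third) dosing intervals.

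The Part 1 SAP keeps this status. In section 4.1.2, the list headed "The primary pharmacokinetic endpoints are" includes half-life on Day 1 and on Day 29. Section 9.2.2 then gives the only working definition of t1/2 in that SAP: "the time at which the concentration is half of the observed maximum concentration within the dosing interval". Section 5.20 counts PK time from the last dose. Section 9.2.2 ends with "PK parameters will be calculated separately by designee of 89bio". Section 10 states: "There are no changes to the planned analysis in the protocol".

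**The concern.** Terminal half-life is a property of the slope at the end of the profile, ln(2)/λz. The SAP quantity is a point in time set by the peak, and it contains no slope. The two agree only when the drug enters the circulation instantly and then declines along a single exponential. BIO89-100 is given subcutaneously, so there is an absorption phase and tmax is greater than zero. Three problems follow:

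- **Ambiguity.** Half of Cmax is normally reached on the way up as well as on the way down, and the SAP does not say which crossing counts. It also gives no rule for interpolating between samples.
- **Bias.** The falling crossing, timed from the dose, adds the time to peak to the time needed to lose half of the peak while absorption is still going on.
- **Missing values.** If the concentration has not halved by the end of the dosing interval, the quantity does not exist. The SAP has no rule for that case.

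At stake is one of the four PK parameters that Part 1 has as primary endpoints. It would appear in the report under a name that it does not deserve.

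**Working it through.** The plan states no half-life value for this endpoint, so there is no figure to reproduce. The check compares the two definitions on the same simulated profile.

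**Inputs**
- Dosing intervals τ = 168 h (QW) and 336 h (Q2W). Day 1 is dose 1; Day 29 is dose 5 (QW) or dose 3 (Q2W). Source: protocol Table 1.
- True terminal half-life: not given for humans. Assumed 50, 75 and 100 h. The only figure in the documents is about 50 h in monkeys (protocol 3.2.4.1).
- tmax after a single dose: not given. Assumed 24, 36 and 48 h.

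**Model.** One compartment with first-order absorption: C(t) ∝ exp(−k·t) − exp(−ka·t), with k = ln(2)/t1/2 and ka solved from tmax = ln(ka/k)/(ka − k). For Day 29 the contributions of the earlier doses are added. The SAP value is the solution of C(t) = Cmax/2.

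**One case in full** (half-life 50 h, tmax 48 h, Day 1)
- k = 0.693/50 = 0.01386 per h. ka = 0.0298 per h, since ln(0.0298/0.01386)/(0.0298 − 0.01386) ≈ 48 h.
- Cmax ∝ exp(−0.665) − exp(−1.430) = 0.514 − 0.239 = 0.275, so half of Cmax is 0.137.
- At 134.1 h: exp(−1.859) − exp(−3.996) = 0.156 − 0.018 = 0.137. This is the falling crossing.
- Ratio to the true half-life: 134.1/50 = 2.68. Counted from tmax: (134.1 − 48)/50 = 86.1/50 = 1.72.
- The rising crossing is at 10.9 h.

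**Falling crossing on Day 1, hours from dose (ratio to true half-life)**

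| True half-life | tmax 24 h | tmax 36 h | tmax 48 h |
|---|---|---|---|
| 50 h | 86 (1.71) | 108 (2.17) | 134 (2.68) |
| 75 h | 108 (1.44) | 128 (1.71) | 151 (2.01) |
| 100 h | 132 (1.32) | 151 (1.51) | 171 (1.71), Q2W only |

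In the last cell the weekly profile ends at 168 h with trough/Cmax = 0.51, so half of Cmax is never reached.

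**All 36 combinations** (9 parameter pairs, QW and Q2W, Day 1 and Day 29)
- Falling crossing from dose: 84 h (QW Day 29, 50 h/24 h) to 171 h; 1.3 to 2.7 times the true half-life.
- Falling crossing counted from tmax: 62 to 123 h; 1.1 to 1.7 times.
- Rising crossing: about 1 to 11 h.
- Not reached within the interval: 1 of 36.
- The SAP value also moves when the true half-life does not. At 50 h/48 h it is 134 h on Day 1, but 128 h on QW Day 29.

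**Other assumptions.** With absorption half-lives of 6, 12, 24 and 40 h in place of fixed tmax values, the single-dose falling crossing is 80 to 251 h (1.35 to 3.5 times). At weekly steady state it is not reached in 3 of 12 scenarios.

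**Why the direction is upward in this model.** With instant input, the half-Cmax time equals ln(2)/k exactly. With absorption, drug is still entering after the peak, so the fall from Cmax is slower than exp(−k·t), and counting from the dose adds tmax on top.

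**The case against.** The strongest reply is that the SAP sentence may never be used. A sponsor designee calculates the parameters, the protocol calls for noncompartmental methods, and protocol section 8 foresees pharmacokinetic analysis plans that were not supplied. The designee may well report a standard terminal half-life. That stands as a limit on certainty: the documents show what the SAP defines, not what will be run. It does not remove the conflict. No other definition of t1/2 appears in the SAP. Either the sentence is followed and the endpoint is biased, or it is ignored and the report departs from its own plan.

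Other points on that side:
- The endpoint is descriptive. No hypothesis, power or sample size rests on it; Cmax, AUC and tmax are unaffected; and individual concentrations are listed, so the right value can be recovered. All of this is true and limits the harm. But the primary PK objective is itself descriptive, so a wrong parameter is a wrong primary result.
- Half-life has an obvious bearing on weekly versus two-weekly dosing, but neither document ties a regimen decision to the t1/2 measured in this study. I rest nothing on that link.
- The Part 1 SAP is "based on study protocol BIO89-100-002 Version 3.0 dated 25 March 2020", and the protocol at hand is a later version. The statement of no changes therefore refers to a text that I cannot check. The SAP quantity is not a terminal half-life under any version.
- Reading the rising crossing as a half-life is strained. I agree that the falling one is the likely intention, but a definition should not leave this open.
- The size depends on assumed kinetics. It does, and it is presented that way.

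**Conclusion.** The concern holds. The Part 1 SAP gives a primary PK endpoint a definition that differs from the one in the protocol and does not declare the change. Followed as written, it yields a value that is too long, ambiguous, or undefined for some profiles. Under the assumed half-lives of 50 to 100 h and tmax of 24 to 48 h, the overstatement is 1.3 to 2.7 times when timed from the dose, and 1.1 to 1.7 times when timed from the peak.

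The textual conflict needs no assumption. The size and the upward direction rest on a one-compartment model with first-order absorption; a marked distribution phase could change both. This should be corrected before the PK summaries are produced. It casts no doubt on the other PK parameters or on any inferential result.

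**What to change.** Replace the t1/2 bullet in section 9.2.2 of the Part 1 SAP with a definition along these lines: *terminal elimination half-life, ln(2)/λz, where λz is minus the slope of a log-linear regression over the terminal phase, using at least three quantifiable concentrations after tmax and stated criteria for fit and time span; not reported when the criteria are not met.* Add that the number of estimable profiles is shown by group and day. Add also that values below the quantification limit are left out of the regression, because section 9.1.4 sets them to zero for analysis and zero has no logarithm. If a separate PK plan already contains such a rule, citing it is enough. If the sponsor also wants the time to half of Cmax, it should carry its own name, specify the falling crossing and its time origin, and be declared in section 10.

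The cost is one bullet and no new samples. Some weekly profiles may not be estimable. With a half-life of 75 to 100 h, the window after tmax covers only about 1.2 half-lives (120/100) to 2 half-lives (144/75 = 1.9). The sampling times are blacked out, so I could not check how many points fall there. The number required is a choice for the sponsor's pharmacokineticist.

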9.3. Study Subjects

Subject enrollment by site will be summarized. The number of subjects who were screened, randomized, early discontinued from investigational product, early discontinued from study, and completers will be summarized.

9.3.1. Subject Disposition

Subject disposition will be presented for the Randomized Analysis set. The number of subjects randomized, included in each analysis population, who completed study or had early terminated from the study and the reason, who completed IP regimen or discontinued IP regimen prematurely and the reason will be summarized by treatment group and overall. The number of subjects who were screened will be summarized based on Screened Analysis Set.

Subject disposition will also be summarized by subgroup of biopsy confirmed NASH.

In addition, a listing will be provided for subjects who had been impacted by COVID-19, eg, study interruptions and the duration of their study interruption, withdrew from investigational product, withdrew from study, or had protocol deviation.

9.3.2. Demographics and Baseline Characteristics

Demographics and baseline characteristics data will be summarized descriptively using Randomized Analysis Set by treatment group and overall. Demographics and baseline characteristics include but not limited to, age (continuous and categories: <65, 65 to <75 and \geq 75 years), sex, race and ethnicity, height, body weight, body mass index (continuous and categories: <25, 25 to <30, 30 to <35, and \geq 35 kg/m²), [REDACTED], central obesity (waist circumference of >102 cm for males, >88 cm for females, or body mass index (BMI) >30 kg/m²); biopsy confirmed NASH (yes/no); [REDACTED]

[REDACTED] triglycerides (continuous and categories: <150, 150 to <200 and \geq 200 mg/dL), non-HDL, HDL-c, LDL-c (continuous and categories: <130, \geq 130 mg/dL), [REDACTED], ALT, increased ALT (ALT \geq 40 U/L in males, ALT \geq 30 U/L in females), AST, adiponectin, Pro-C3, Pro-C3 subgroup (<14.71, \geq 14.71 ng/mL), [REDACTED] [REDACTED], subjects meeting at least one or two out of the following five criteria: baseline ALT >1x ULN, VCTE \geq 7.6 kPa, ELF \geq 7.7, Pro-C3 \geq 14.71 ng/mL, FIB-4 score > 1.3. FFA, adipo-IR, hsCRP, MRI-PDFF, [REDACTED] [REDACTED], endogenous FGF21, type 2 diabetes mellitus history (yes/no), HbA1c, HOMA-IR, fasting plasma glucose, [REDACTED]

[REDACTED] The criteria where the subjects qualified for the study, eg, 1) NASH with fibrosis (stages F1, F2 or F3) or 2) Central obesity with T2DM or 3) Central obesity WITH either increased ALT and/or Fibroscan VCTE score \geq 7 KPa per protocol definitions will also be summarized.

Demographics and baseline characteristics summary will be repeated by subgroup of “biopsy confirmed NASH with fibrosis status (F1, F2, F3)” (yes/no).

9.3.3. Biopsy History

The number and percentage of subjects with biopsies within 24 months of screening will be summarized by fibrosis stage (F0, F1, F2, F3, F4), NAFLD activity score (continuous with range, categorical: score from 0 to 8), steatosis score (continuous with range, categorical), ballooning degeneration score (quartiles, categorical), lobular inflammation score (continuous with range, categorical). The percentages for this table will be based on the number of subjects with biopsies within 24 months.

9.3.4. Medical History

The number and percentage of subjects will be summarized by medical history code (System organ class and preferred term) and by treatment group and overall for the Randomized Analysis set. Medical history will be coded by Medical Dictionary for Regulatory Activities (MedDRA version 23.0 – Apr 2020).

9.3.5. Inclusion/Exclusion Criteria

Inclusion and exclusion criteria failures will not be summarized, but will be listed for the Screened Analysis set.

9.3.6. Investigational Product Administration

Investigational product administration data such as the number and percentage of subjects who were administered full doses of investigational product each time, the number and percentage of subjects who were administered at least one partial dose, total number of injections administered over the study, investigational product exposure and investigational product compliance over the entire study will be summarized for the Safety Analysis set.

All investigational product administration data including injection site, incomplete injections their volumes and reason for incompleteness, full or partial doses administered and total volume of injections will be listed by visit.

9.3.7. Concomitant Medication

The World Health Organization Drug Dictionary (B3 WHO Drug Global – Mar 2019) will be used to code the verbatim descriptions of prior and concomitant medications into the Anatomic Therapeutic Chemistry (ATC) classification system. Each verbatim name will be classified by anatomical main group, ATC level 1, therapeutic subgroup, ATC level 2, pharmacological subgroup, ATC level 3, and chemical subgroup, ATC level 4.

The number and percentage of subjects receiving concomitant medications will be summarized by treatment group and ATC classification level 2 and level 4 for the Safety Analysis set.

Pre-treatment medications will not be summarized, but will be in listings.

Baseline medications will also be summarized by ATC classification level 2 and 4.

9.3.8. Concomitant Procedures

All procedures, pre-treatment and concomitant, will be listed.

9.3.9. Protocol Deviations

Important protocol deviations will be summarized by treatment group for the Randomized Analysis set. All protocol deviations will be reviewed by study team to identify notable deviations prior to database lock. All protocol deviations will be listed.

